8.5 Assessment of Causal Relationship

The investigator will assess the relationship of an adverse event to study product as related or not related (ie, if there is a reasonable possibility that the study product caused the event) and document the relationship in the subject's source documents.

8.6 Assessment of Severity (Intensity)

Severity describes the intensity of a specific adverse event (eg, mild, moderate, severe, life-threatening, or death). The particular event may be of relatively minor medical significance (such as severe headache). Severity is not the same as “serious,” which is based on subject/event outcome or action criteria.

Investigators will grade the severity of adverse events. The severity of an adverse event is to be recorded on the case report form and in the subject’s source documents.

Two different severity grading systems will be used depending on type of adverse event: systemic allergic reactions including anaphylaxis, or all other adverse events. Brief descriptions of the 2 severity grading systems are provided.

Severity of systemic allergic reactions, including anaphylaxis, will be graded using the systemic allergic reaction grading system, with scores ranging from 1 (mild) to 5 (death) ([Table 9](#)). The protocol criteria for systemic allergic reaction are provided in [Section 8.4](#). The term *anaphylaxis* is used to describe the subset of systemic allergic reactions that meet the criteria in [Table 8](#) and are grade 3 or higher per the systemic allergic reaction grading system ([Table 9](#)). The clinical assessment of anaphylaxis is described in [Section 8.4.1](#).

Table 9: Systemic Allergic Reaction Grading System

Grade 1 Mild	Grade 2 Moderate	Grade 3 Severe	Grade 4 Life-Threatening	Grade 5 Death
Systemic allergic reaction including any of the following signs and symptoms from 2 or more body systems: 
 Cutaneous: generalized pruritus, generalized urticaria, generalized flushing, angioedema (not laryngeal) Conjunctival: injection or pruritus Upper airway: rhinitis, cough (unrelated to laryngeal edema or bronchospasm) Gastrointestinal: nausea, mild abdominal pain, vomiting, or diarrhea 	Systemic allergic reaction involving 1 or more of the following: 
 Lower airway: (wheezing, chest tightness, dyspnea) Gastrointestinal: moderate abdominal pain or persistent vomiting or diarrhea 	Systemic allergic reaction involving 1 or more of the following: 
 Upper airway: laryngeal edema with stridor Lower airway: (wheezing, chest tightness, dyspnea) with cyanosis or hypoxia (O_2 saturation $\leq 92\%$) Cardiovascular: clinically significant hypotension [1] without end-organ dysfunction 	Systemic allergic reaction involving 1 or more of the following: 
 Lower airway: respiratory compromise (dyspnea, wheeze, bronchospasm, hypoxemia) requiring mechanical support Cardiovascular: hypotension [1] with associated symptoms of end-organ dysfunction (eg, hypotonia [collapse], syncope) 	Death

The protocol criteria for systemic allergic reaction are provided in [Section 8.4](#). The site of allergen exposure should be considered during the assessment of a systemic versus local reaction.

[1] Reduced blood pressure after exposure to a known allergen for the subject (minutes to hours) as follows:
 Infants and children: $> 30\%$ decrease from baseline in systolic blood pressure or low systolic blood pressure defined as follows:

- Age 1-10 years: $< (70 \text{ mm Hg} + [2 \times \text{age}])$
- Age 11-17 years: $< 90 \text{ mm Hg}$

 Adults: (age ≥ 18 years): systolic blood pressure $< 90 \text{ mm Hg}$ or $> 30\%$ decrease from baseline

Severity of all other adverse events (including adverse events considered allergic reactions that are not systemic allergic reactions) will be graded according to the general adverse event grading system. Adverse events will be graded 1 to 5 and have unique clinical descriptions of severity for each adverse event based on the general guideline presented in [Table 10](#). Full details of the general adverse event grading system are provided in the study manual.

Table 10: General Adverse Event Grading System

Grade 1 Mild	Grade 2 Moderate	Grade 3 Severe	Grade 4 Life-Threatening	Grade 5 Death
Mild symptoms causing no or minimal interference with usual social and functional activities with intervention not indicated	Moderate symptoms causing greater than minimal interference with usual social and functional activities with intervention indicated	Severe symptoms causing inability to perform usual social and functional activities with intervention	Potentially life-threatening symptoms causing inability to perform basic self-care functions with intervention indicated to prevent permanent impairment, persistent disability, or hospitalization indicated	Death

8.7 Special Safety Considerations

This section provides guidelines for the assessment of allergic reactions (including tolerability of a dose), treatment for allergic reactions, study product dose adjustments due to allergic reactions or other reasons, missed doses of study product, adverse events of interest, and other notable events (overdose, pregnancy and other reproductive considerations). The assessment and treatment for allergic reactions resulting from accidental and nonaccidental food allergen exposure should follow the same guidelines as allergic reactions resulting from study product.

8.7.1 Assessment of Allergic Reactions

Allergy symptoms (allergic reactions) are expected during treatment with study product, consistent with other desensitization studies. Subjects must be observed for at least 90 minutes after completion of a dose or dose escalation at the study site, with measurements of blood pressure and heart rate, and assessment for symptoms of allergic reaction performed 15 to 30 minutes postdose and approximately every 30 minutes thereafter.

The length of observation will be extended beyond 90 minutes if symptoms of allergic reaction develop as follows:

- Mild symptoms: observe for 90 minutes or at least 1 hour after symptoms resolve, whichever is longer.
- Moderate symptoms: observe for at least 2 hours after symptoms resolve.

- Severe symptoms: observe for at least 3 hours after symptoms resolve either at the study site or an emergency facility, as appropriate. Consider extended overnight observation if symptoms are protracted.
- Life-threatening symptoms: observe at an emergency facility for as long as needed consistent with good medical practice. Consider extended overnight observation if symptoms are protracted.

The assessing physician will determine whether the allergy symptoms meet the criteria for dose-limiting symptoms ([Section 8.7.1.1](#)).

The severity of symptoms of an allergic reaction will be assessed as described in [Section 8.6](#).

Signs and symptoms of allergic reactions will be recorded on the case report form and in the subject's source documents.

8.7.1.1 Assessment of the Tolerability of a Study Product Dose or Dose Level

The tolerability of a study product dose or dose level will be assessed based on the occurrence of acute allergy symptoms (allergic reactions) after dosing. When multiple symptoms are present, the severity of the most severe symptom will be used to determine whether symptoms are dose limiting and the dose or dose level is tolerated. Possible assessments of symptom severity, dose-limiting symptoms, and dose tolerability are shown in [Table 11](#).

Table 11: Allergy Symptom Severity and Study Product Dose Tolerability

Symptom Severity	Dose-Limiting Symptom	Assessed Tolerability of Dose
None	No	Tolerated
Mild, oropharyngeal symptoms only	No	Tolerated
Mild, meeting tolerability criteria	No	Tolerated
Mild, not meeting tolerability criteria	Yes	Not tolerated
Moderate, with rare exceptions	Yes	Not tolerated
Severe	Yes	Not tolerated
Life-threatening	Yes	Not tolerated

No Symptoms: A study product dose associated with no symptoms will be assessed as tolerated.

Mild symptoms: For a study product dose associated with mild symptoms, investigator assessment is essential in determining if the symptoms are dose limiting. Mild symptoms are not dose limiting if they meet all of the tolerability criteria as follows:

- Are isolated to a single organ system
- Resolve with no medications or with \leq 2 doses of oral antihistamine
- Do not require administration of epinephrine
- Do not worsen in intensity or distribution over time
- Resolve or show definite signs of resolving in under 1 hour
- Do not include objective wheezing

The study product dose is to be considered not tolerated if mild symptoms do not meet the tolerability criteria as follows:

- Occur in 2 or more organ systems
- Require treatment with \geq 3 doses of oral antihistamine or \geq 1 dose of epinephrine
- Progress in severity or distribution over time
- Do not resolve or show definite signs of resolving in under 1 hour
- Include objective wheezing

If a study product dose associated with mild symptoms that do not meet the tolerability criteria is assessed as tolerated by the investigator, an explanation must be provided in the subject's source documents.

Recurrent mild symptoms during several days of dosing at home suggest that the study product dose level is likely not tolerated, even if the symptoms meet the tolerability criteria. For mild dose-related symptoms occurring \geq 7 times within 2 weeks, the dose level is to be considered not tolerated. Isolated mild oropharyngeal pruritus occurring \geq 7 times within 2 weeks may not lead to an assessment of not tolerated for the dose level; tolerability of the dose level should be discussed with the medical monitor.

Moderate symptoms: A study product dose associated with moderate symptoms will be assessed as not tolerated, except on rare occasions such as a transient, self-limited symptom in a single organ system that requires no intervention, resolves completely, and is typically subjective.

If a study product dose associated with moderate symptoms is assessed as tolerated by the investigator, an explanation must be provided on the case report form.

Severe symptoms: A study product dose associated with severe symptoms will be assessed as not tolerated.

Life-threatening symptoms: A study product dose associated with life-threatening symptoms will be assessed as not tolerated.

8.7.2 Treatment of Allergic Reactions After Study Product Dosing

Treatment of allergic reactions after study product dosing is guided by the type of symptoms and severity as determined by the investigator and should follow routine medical practice and professional practice guidelines, including the prompt use of epinephrine when indicated. Symptomatic treatment should be used to supplement dose reduction and not as a substitute for it. Rescue medications for acute allergic reactions include antihistamines, epinephrine, IV fluids, beta-agonists (eg, albuterol by inhaler or nebulizer), oxygen, and glucocorticosteroids as indicated ([Section 7.3](#)). Treatment for chronic or recurrent allergic reactions should be used minimally and discontinued as soon as clinically appropriate. Treatment for chronic or recurrent allergic reactions should not be started in advance of symptoms; however, exceptions may be allowed on a case-by-case basis following discussion with the medical monitor.

A medical monitor will be available to answer questions or to assist in decisions related to the study protocol.

8.7.3 Dose Adjustment of Study Product for Allergic Reactions

[figure not shown]
8.7.3.1 Dose Adjustment of Study Product During Initial Dose Escalation (Days 1 and 2)

Actions that may be taken with study product for allergic reactions occurring on day 1 of initial dose escalation are guided by the severity of the allergic reactions and include the following:

- Extend the time interval between study product doses (up to an additional 30 minutes) without any additional treatment.
- Initiate enhanced clinical monitoring (eg, more frequent vital sign monitoring [including respiratory rate], auscultation, oxygen saturation level).
- Treat with antihistamine and resume study product dose escalation within 60 minutes after the previous dose, if assessed as safe.
- Treat with epinephrine, beta-agonist, oxygen, IV fluids, > 2 doses of antihistamines, and/or glucocorticosteroids as necessary. Stop the initial dose escalation and discontinue the subject early from the study if these rescue medications are used at ≤ 1 mg study product or for severe symptoms at the 2 mg dose ([Section 5.3](#)).
- Stop the initial dose escalation and discontinue the subject early from the study.

The process algorithm for actions to be taken with study product dosing and treatment for acute symptoms on initial dose-escalation day 1 is shown in [Figure 2](#) and described in [Table 12](#). The same process algorithm for actions to be taken with study product dosing and treatment for acute symptoms is to be followed for allergic reactions occurring on day 2 of initial dose escalation, with the exception that only 1 dose will be administered on day 2.

Figure 2: Management of Study Product Dosing for Allergy Symptoms on Initial Dose-Escalation Day 1

Assess dose tolerability per [Section 8.7.1.1](#).

Table 12: Description of Actions to Be Taken With Study Product Dosing for Allergy Symptoms on Initial Dose-Escalation Day 1

Symptoms	Actions
Mild	
For oral/pharyngeal pruritus occurring in isolation, advance to the next dose of study product in 30 minutes.
 
For other mild symptoms, either:
 
 Advance to the next dose of study product in 30 to 60 minutes. Treat with antihistamine, then resume dose escalation within 60 minutes after the previous dose if signs and symptoms resolve to minimal or residual, and the investigator considers continued dosing to be safe. 
If only 1 or 2 doses of antihistamine are used to treat mild symptoms, the initial dose escalation may continue.
 
If a second medication (eg, epinephrine or a beta-agonist) or > 2 doses of antihistamines are needed, stop the initial dose escalation and discontinue the subject early from the study, even if the symptoms are assessed as mild.
 
Use of epinephrine, although unlikely to be used to treat mild dose-related symptoms, will stop the initial dose escalation and discontinue the subject early from the study.

Moderate	
For moderate symptoms not worsening in intensity or distribution over time, the investigator may take a stepwise approach to treatment. Treatment may be initiated immediately or after observation. If the first action is observation, observation should not exceed 30 minutes before starting treatment if symptoms have not resolved. Initiate treatment with antihistamines or administer epinephrine immediately as appropriate. Initiate other therapies sequentially or concurrently per investigator judgment.
 
For moderate symptoms occurring at ≤ 1 mg study product, stop the initial dose escalation and discontinue the subject early from the study.

Severe	
For severe symptoms at any dose, administer the appropriate rescue medications and treatment per standard of care. Stop the initial dose escalation and discontinue the subject from study early.

Life-threatening	
For life-threatening symptoms at any dose, administer the appropriate rescue medications and treatment per standard of care. Stop the initial dose escalation and discontinue the subject from study early.

Assess dose tolerability per [Section 8.7.1.1](#).

Treatment with epinephrine, beta-agonist, oxygen, IV fluids, > 2 doses of antihistamines, and/or glucocorticosteroids at ≤ 1 mg study product or for severe symptoms at the 2 mg dose on initial dose-escalation day 1 or 2 will stop the initial dose escalation and discontinue the subject early from the study ([Section 5.3](#)).

IV, intravenous.

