5.2.3.1 Initial Dose-Escalation Procedures

Initial dose-escalation procedures are listed in [Appendix 5](#). Subjects may have clear liquids or flavored gelatin during the dosing procedures.

Day 1

Subjects will be required to discontinue antihistamines and other medications that could interfere with the assessment of an allergic reaction for 5 half-lives of the medication before the first day of dose escalation.

Study product will be administered in 5 increasing doses in a stepwise manner in 20- to 30-minute intervals as tolerated. The 5 doses and cumulative dose of study product to be consumed on day 1 are shown in [Table 1](#).

Table 1: Study Product Single Doses and Cumulative Dose on Day 1

Dose Number	Study Product Dose (mg)	Cumulative Dose (mg)
1	0.2	0.2
2	0.4	0.6
3	0.8	1.4
4	1	2.4
5	2	4.4

The time points for study product dosing and assessments of blood pressure, heart rate, temperature, and allergic reaction are provided in [Table 2](#). Subjects who develop dose-limiting or moderate allergy symptoms at ≤ 1 mg doses of study product, severe symptoms at any dose, or use rescue medications (except ≤ 2 doses of antihistamines, [Section 8.7.3.1](#)) at ≤ 1 mg doses of study product or for severe symptoms at the 2 mg dose will stop dose escalation and discontinue early from the study ([Section 5.3](#)).

Table 2: Initial Dose-Escalation Day 1 Procedures

Study Product Dose (Timing) Time Point	Administer Study Product	Blood Pressure	Heart Rate	Temp	Assess Allergy Symptoms
Predose		X	X	X	
0.2 mg	X				
15-30 min postdose		X	X		X
0.4 mg (20-30 min after previous dose) [1]	X				
15-30 min postdose		X	X		X
0.8 mg (20-30 min after previous dose) [1]	X				
15-30 min postdose		X	X		X
1.0 mg (20-30 min after previous dose) [1]	X				
15-30 min postdose		X	X		X
2 mg (20-30 min after previous dose) [1]	X				
15-30 min postdose		X	X		X
Approximately every 30 min until at least 90 min after last dose or end of observation per allergy symptoms [2]		X	X		X

[1] If the previous dose was tolerated ([Section 8.7.1.1](#)). If the subject has dose-limiting or moderate allergy symptoms anytime at ≤ 1 mg, severe symptoms at any dose, or requires rescue medications (except ≤ 2 doses of antihistamines, [Section 8.7.3.1](#)) at ≤ 1 mg or for severe symptoms at 2 mg, stop dose escalation and discontinue the subject early from the study. If 1 mg is tolerated or no more than mild or moderate symptoms occur at 2 mg, the subject will return for a single 1 mg dose on day 2.

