[2] The length of observation is based on signs/symptoms of allergic reaction per [Section 8.7.1](#).

Min, minutes; temp, temperature.

Day 2

Subjects who tolerate at least 1 mg study product and have no more than mild or moderate allergy symptoms at the 2 mg dose on day 1 will return to the study site on day 2 to receive a single 1 mg dose under medical supervision. Day 2 should be the next consecutive day after day 1. If circumstances create a safety risk (eg, an intercurrent illness), day 2 may be delayed after discussion with the medical monitor. Subjects who tolerate the 1 mg dose with no more than mild symptoms that are not dose-limiting will receive an adequate supply of study product to continue daily dosing at home at 1 mg/day during up-dosing ([Section 5.2.3.2](#)).

Subjects who develop moderate or severe symptoms after consuming the 1 mg dose on day 2, or use rescue medications (except ≤ 2 doses of antihistamines, [Section 8.7.3.1](#)), will stop study product dosing and discontinue early from the study ([Section 5.3](#)).

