Adverse event or intercurrent illness	
Subjects must discontinue early for any intolerable adverse event that may lead to undue risk if study treatment were continued, such as the following:
 
 • Life-threatening symptoms, including anaphylaxis resulting in hypotension, neurologic compromise, or mechanical ventilation related to study treatment or food challenge. • Severe dose-related symptoms that require intensive therapy (per investigator assessment, but may include interventions such as IV epinephrine, intubation, or admission to an intensive care unit) or are recurrent. 
Subjects must discontinue early for any adverse event that meets the early discontinuation criteria for study product tolerability or delays as follows:
 
 • Tolerability of study product: 
 – Dose-limiting or moderate symptoms at ≤ 1 mg or severe symptoms at any dose on initial dose-escalation day 1; dose-limiting, moderate, or severe symptoms on initial dose-escalation day 2 – Unable to reach the 300 mg/day dose within 40 weeks of up-dosing • Use of rescue medications: 
 – Treatment with epinephrine, beta-agonist, oxygen, IV fluids, > 2 doses of antihistamines, and/or glucocorticosteroids at ≤ 1 mg study product or for severe symptoms at the 2 mg dose on initial dose-escalation day 1 or 2 – Treatment with 3 or more doses of epinephrine for an event of dose-related symptoms anytime • Dose adjustment of study product: 
 – Unable to escalate the dose level after 3 consecutive failed attempts with at least 2 weeks between each escalation attempt – Unable to tolerate 3 attempts at dose reduction after mild or moderate symptoms, or unable to tolerate 1 attempt at dose reduction after severe symptoms • Missed ≥ 15 consecutive days of study product dosing due to any circumstances (eg, as part of the treatment for an intercurrent adverse event). Missed doses per dose adjustment guidelines in Section 8.7.3.2 are allowed. 
Subjects must discontinue early for any intolerable adverse event that cannot be ameliorated using adequate medical intervention or that in the opinion of the investigator or sponsor may lead to undue risk if study treatment were continued, such as the following:
 
 • Poor control or persistent activation of secondary atopic disease (eg, atopic dermatitis, asthma). • Development of biopsy-documented eosinophilic esophagitis.

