Mild	
For oral/pharyngeal pruritus occurring in isolation, continue the study product dose level at home for the 2-week dosing interval, unless other symptoms develop.
 
For other mild symptoms and if the study product dose is assessed as tolerated (Section 8.7.1.1), repeat the same dose level the next day, ideally at the study site although it may be given at home.
 
 • If no symptoms occur with the repeated dose, continue the dose level for the 2-week dosing interval. • If mild symptoms occur with the repeated dose and the dose is assessed as tolerated, continue the same dose level or reduce the dose to the previous tolerated dose level for the 2-week dosing interval. 
For other mild symptoms and if the study product dose is assessed as not tolerated (Section 8.7.1.1), the next dose is to be the previous tolerated dose level and given at the study site.
 
 • If the reduced dose is tolerated, continue the dose level for at least 1 to 2 weeks. • If the reduced dose is assessed as not tolerated, the next dose is to be reduced 1 or 2 dose levels and given at the study site. 
 – If the second reduced dose is tolerated, continue this dose level for the 2-week dosing interval. – If the second reduced dose is assessed as not tolerated, discuss early discontinuation with the medical monitor. – If a third reduced dose is considered to be safe after discussion with the medical monitor, give it at the study site under medical supervision. If the dose is assessed as not tolerated, stop study product dosing and discontinue the subject early from the study (Section 5.3). 
For other mild symptoms and if the study product dose tolerability is uncertain, follow the general guidance in this table for chronic or recurrent mild symptoms.

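### Table 12's mild row gives no action for mild symptoms that are dose-limiting at day-1 doses of 1 mg or less, and conflicts there with Section 5.2.3.1, Table 2 footnote [1] and Table 4

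*Protocol*

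**What the plan says.** **Classification.** Section 8.7.1.1 sets criteria that mild symptoms must all meet for a dose to count as tolerated. If they are not all met, the text below Table 11 reads: "The study product dose is to be considered not tolerated if mild symptoms do not meet the tolerability criteria as follows". The failing features are involvement of two or more organ systems, three or more oral antihistamine doses or any epinephrine, progression, no resolution or clear sign of it within 1 hour, and objective wheezing. Table 11 classes mild symptoms that fail as dose-limiting and the dose as not tolerated. The investigator may still assess the dose as tolerated, with an explanation in the source documents.

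**Consequence on day 1.** Section 5.2.3.1 stops escalation and discontinues "Subjects who develop dose-limiting or moderate allergy symptoms at ≤ 1 mg doses of study product, severe symptoms at any dose". Table 2 footnote [1] repeats this, and also makes each next dose conditional on the previous one having been tolerated. Table 4 lists as grounds for mandatory discontinuation: "Dose-limiting or moderate symptoms at ≤ 1 mg or severe symptoms at any dose on initial dose-escalation day 1".

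**Action table for day 1.** Section 8.7.3.1 gives Figure 2 and Table 12 as the algorithm. For mild symptoms beyond isolated oral or pharyngeal itching, Table 12 offers "Advance to the next dose of study product in 30 to 60 minutes" or antihistamine followed by resumption. Its stopping rule is "If a second medication (eg, epinephrine or a beta-agonist) or > 2 doses of antihistamines are needed, stop the initial dose escalation"; epinephrine use also stops escalation. A footnote says "Assess dose tolerability per" Section 8.7.1.1.

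**Day 2.** The stopping sentence in Section 5.2.3.1 covers "Subjects who develop moderate or severe symptoms after consuming the 1 mg dose on day 2, or use rescue medications". Table 4 also lists dose-limiting symptoms for day 2.

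**The concern.** Table 12 is the table a site would consult while a subject is reacting. Its mild row is not divided by whether the dose was tolerated, and its only stopping triggers are medications. The discontinuation rules elsewhere turn on whether symptoms are dose-limiting, which mild symptoms can be with no medication at all.

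Two things are at stake. This is supervised first exposure in a first-in-human study (Section 1.2) at about 30 sites (Section 3.1), so sites could handle the same reaction differently. And day-1 discontinuation feeds the primary endpoint: a subject who has taken any part of a dose is in the ITT population (Section 10.2) and, if discontinued before the exit challenge, is a nonresponder (Sections 10.3 and 10.5.1). Some day-1 attrition would then depend on which table the site followed.

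**Working it through.** The protocol gives no figure to reproduce on this point, so the check is a comparison of passages, with one line of arithmetic for scale.

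**Step 1: a test case.** A subject has mild symptoms in two organ systems after a day-1 dose of 1 mg or less (0.2, 0.4, 0.8 or 1 mg in Table 1), with no medication or one to two antihistamine doses. This is a realistic case: Table 9 itself defines a grade 1 (mild) systemic reaction by signs from two or more body systems.

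| Passage | Result for this subject |
|---|---|
| Section 8.7.1.1 and Table 11 | Dose-limiting; dose not tolerated, unless the investigator documents otherwise |
| Table 2 footnote [1] | No next dose; discontinue |
| Section 5.2.3.1, day 1 | Stop escalation; discontinue |
| Table 4 | Discontinue |
| Table 12, mild row | Advance, or antihistamine and resume; no stopping trigger met |

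**Step 2: the other failing features.**
- *Medication use* (three or more antihistamine doses, or epinephrine): at 1 mg or less, Table 12 and the other passages all stop. No conflict.
- *Progression*, or *objective wheezing*, in symptoms still graded mild: Table 12 has no trigger for either. Conflict.
- *No sign of resolving within 1 hour*: the antihistamine option requires symptoms to have subsided to a minimal or residual level and the investigator to think further dosing safe, so that option does not clear this subject. The untreated option has no such condition, and its window opens at 30 minutes, before the 1-hour criterion can be judged. Conflict on that option.

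**Step 3: comparison with up-dosing.** Table 13 carries the same instruction to assess tolerability, yet its mild row has a separate branch, beginning "For other mild symptoms and if the study product dose is assessed as not tolerated", with its own actions. Table 12 has no counterpart.

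**Step 4: day 2.** Only one dose is given, so there is no next dose to advance to. The paragraph before the stopping sentence allows continued dosing only when symptoms are at most mild and not dose-limiting, and Section 3.1 discontinues subjects who do not tolerate 1 mg. What remains is one sentence that omits a reason listed in Table 4.

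**Step 5: scale.** Planned AR201 arm: 56 (Section 10.3). One subject who would have responded if continued, but is discontinued on day 1, changes the ITT response rate by 1/56 = 0.0179, or 1.8 points. The planned difference is 60% − 25% = 35 points, so one such subject is 1.8/35, about 5% of it.

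**The case against.** The strongest reply is that the passages should be read together. Day-1 doses are given only as tolerated, Table 2 conditions each further dose on tolerance of the previous one, and the assessing physician decides whether symptoms are dose-limiting (Section 8.7.1). Both Figure 2 and Table 12 point to Section 8.7.1.1, and the list of possible actions in Section 8.7.3.1 includes stopping. On that reading tolerability is judged first, and the mild row applies only to tolerated doses. The investigator may also document such a dose as tolerated, so discontinuation is not automatic. Figure 2 is not shown and may contain the missing split.

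Much of this stands, and it makes the conflict milder. It does not remove it. The footnote asks for an assessment, but the row gives no action when the answer is not tolerated. Table 2's condition is one side of the disagreement. The override requires a written assessment, whereas Table 12 lets the site advance without one. Even a correct Figure 2 would leave the text of Table 12 at odds with it.

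Three stronger readings are not supported. A reader might infer that Table 12 advances the dose after any mild symptom; it does not, since it stops for a second medication, more than two antihistamine doses, or epinephrine, and advancing is one of two options. A reader might also see the same defect on day 2; Step 4 shows only an incomplete sentence. Finally, a reader might assume that 5% to 15% of the AR201 arm is affected (3 to 8 subjects) and that 60% of them would respond, giving 1.8/56 = 3.2 to 4.8/56 = 8.6 points. The protocol gives no such incidence. The 60% is its assumed maximum for the whole arm and may be too high for subjects who react at these doses, and the calculation ignores the override.

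**Conclusion.** The point holds as an internal inconsistency confined to mild symptoms at day-1 doses of 1 mg or less that are dose-limiting for reasons other than medication use, and that are untreated or treated with one to two antihistamine doses. There, Table 12's mild row lets escalation continue, while Section 5.2.3.1, Table 2 footnote [1] and Table 4 discontinue the subject. On day 2 the issue is limited to one stopping sentence that is narrower than Table 4.

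The effect on the primary analysis is up to 1.8 points of AR201 response per affected subject. That maximum assumes 56 AR201 subjects, a subject who would have responded if continued, and no documented override. The total effect cannot be stated, because the number of such subjects cannot be estimated from the protocol. Correction is warranted by the need for one rule at first exposure, whatever that number is. Nothing here says which rule is clinically right.

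**What to change.** Reconcile Table 12's mild row, and Figure 2 if needed, with Section 8.7.1.1, Section 5.2.3.1, Table 2 footnote [1] and Table 4. Split the row into dose-limiting and not dose-limiting mild symptoms, as Table 13 already splits by tolerability, and make explicit how the documented investigator override fits in. Align the day-2 stopping sentence in Section 5.2.3.1 with Table 4. Every passage should then lead to the same action for the same reaction; which action that is belongs to the sponsor's clinical team.

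The cost is a wording change in the protocol and matching site materials. It adds no procedure and does not alter the sample size or the analysis.
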